8.4.3 Withdrawal and Replacement of Subjects

8.4.3.1 Criteria for Subject Withdrawal

In accordance with the Declaration of Helsinki (Appendix 1) and other applicable regulations, a subject has the right to withdraw from the study at any time for any reason without prejudice to his or her future medical care by the physician or at the institution.

Subjects may withdraw from the study/schedule of assessments for any of the following reasons:

- Adverse Event. The patch treatment will be temporary discontinued for any subject with Grade 4 local skin reactions possibly, probably, or definitely related to the investigational product.
- A subject will be discontinued from further participation in the study for >2 grade 4 local skin reaction possibly, probably or definitely related to investigational product

- The Investigator decides that it is the subject's best interest to be withdrawn from the study.
- The subject is unwilling to continue in the study (consent withdrawal).
- Lack of compliance with protocol requirements and procedures.
- The Sponsor- Investigator or Regulatory Authorities, for any reason, stops the study.
- The subject fails to return to the clinic for scheduled visits and does not respond to telephone or written attempts at contact (lost to follow-up).
- Subject's death

The reason for withdrawal will be recorded in the clinical records and the electronic Case Report Form (eCRF) and reported annually in the IND Annual Report (21 CFR 312.33). All subjects who are withdrawn or discontinue should be provided with alternative medical care, if applicable.

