8.5.6 Dose Adjustments and Dose Escalation

No dose adjustments or dose escalation are planned apart from the adjustment in the duration of application during the first weeks of treatment.

Even though the subjects should ideally reach the daily 24-hour application regimen from the 15th day of patch application onwards, for subjects who may experience some severe local reactions at the initiation of the treatment, the daily duration of patch application should be adapted/reduced if necessary, to limit the severe reactions.

In case of local unbearable skin reactions or in case of systemic allergic reactions, the Viaskin® patch should be removed immediately in order to allow the reactions to subside rapidly. The next patch would be re-applied only the following day at the expected time and the reactions will be observed. If or when the local severe reactions recur, the patch can be removed at that time. This process can be repeated the following days until the time the subject can bear the patch for 24 hours a day.

If a subject is having systemic symptoms including worsening of EoE symptoms, the subject will have return for study visit and possible decrease in daily exposure to the Viaskin patch with gradually increase in exposure as tolerated.

Only one dose is being investigated in this pilot study, at the highest dose of Viaskin Milk currently under development (500 µg of cow's milk proteins) due to the limited number of subjects to be recruited.

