12. SAFETY MEASUREMENTS AND VARIABLES

12.1 Adverse Events Definition

An AE is any untoward medical occurrence that does not necessarily have a causal relationship with the investigational medicinal product. An AE can therefore be any unfavorable or unintended sign, including an abnormal laboratory finding, symptom or disease temporally associated with the use of an investigational medicinal product whether or not considered related to the investigational medicinal product.

AEs will be monitored throughout the entire study. Investigators will ask the subject at each visit if they have experienced any untoward effects since the last study visit. All AEs will be recorded on the eCRFs provided. A description of the event, severity, time of occurrence, duration, any action

(e.g. treatment and follow up tests) and the outcome should be provided along with the Investigator's assessment of the relationship to the study treatment.

AEs will be recorded from the time written screening informed consent is signed until the time of the End of Study visit. AEs still ongoing at the time of End of study visit will be followed for an additional period to encompass a total period of 14 days of AE follow-up after administration of the last dose of treatment.

If known, the name or diagnosis of the illness should be recorded, rather than a listing of individual signs or symptoms. AEs must be graded as being mild, moderate or severe and their start and end dates given. Definitions of severity are as follows:

- Mild:** an AE usually transient in nature and generally not interfering with normal activities
- Moderate:** an AE that is sufficiently discomforting to interfere with normal activities;
- Severe:** an AE that is incapacitating and prevents normal activities.

Even if the Investigator feels there is no relationship to the study drug, all adverse experiences MUST be recorded in the eCRF. The Investigator is requested to assess the relationship of any clinical adverse experience to treatment using the following definitions:

Unrelated: those AEs which are clearly and incontrovertibly due to extraneous causes (concurrent drugs, environment etc.) and do not meet the criteria for drug relationship listed under Unlikely, Possible, Probable or Related.

Unlikely: an adverse experience may be considered unlikely if it includes at least the first two features:

- It does not follow a reasonable temporal sequence from administration of the drug.

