- It could readily have been produced by the subject's clinical state, environmental or toxic factors, or other modes of therapy administered to the subject.
- It does not follow a known pattern to the suspected drug.
- It does not reappear or worsen when the drug is re-administered.

Possible: an adverse experience may be considered possible if it includes at least the first two features:

- It follows a reasonable temporal sequence from administration of the drug.
- It could readily have been produced by the subject's clinical state, environment or toxic factors, or other modes of therapy administered to the subject.
- It follows a known response pattern to the suspected drug.

Probable: an adverse experience may be considered probable if it includes at least the first three features:

- It follows a reasonable temporal sequence from administration of the drug.
- It could not be reasonably explained by the known characteristics of the subject's clinical state, environmental or toxic factors or other modes of therapy administered to the subject.

- It disappears or decreased on cessation or reduction in dose. There are exceptions when an AE does not disappear upon discontinuation of the drug (e.g. bone marrow depression, fixed drug eruptions, tardive dyskinesia, etc).
- It follows a known pattern of response to the suspected drug.

Related: an adverse experience may be considered related if it includes all of the following features:

- It follows a reasonable temporal sequence from administration of the drug.
- It could not be reasonably explained by the known characteristics of the subject's clinical state, environmental or toxic factors or other modes of therapy administered to the subject.
- It disappears or decreased on cessation or reduction in dose. There are exceptions when an AE does not disappear upon discontinuation of the drug. For example: bone marrow depression, fixed drug eruptions, tardive dyskinesia, etc.
- It follows a known pattern of response to the suspected drug.
- It reappears or worsens if the drug is re-administered.

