13.6.6.1 Adverse Events

All AEs will be coded by system organ class and preferred term using MedDRA. Treatment-emergent AEs (TEAEs) will be defined as any AEs, regardless of relationship to study drug, which occur during AE collection period of study drug or any event already present that worsens in either intensity or relationship to study drug following exposure to the Viaskin®. If relationship information is missing, the TEAE will be considered drug-related.

An overall summary of TEAEs will be provided showing the number and percentage of subjects in each treatment group with any TEAE, any potentially drug-related TEAE, any severe TEAE, any serious TEAE, any TEAE leading to discontinuation, and any TEAE leading to death. The number of events will also be presented.

The number of AEs as well as the number and percentage of subjects who experienced at least one AE will be summarized by system organ class, preferred term and treatment group. The incidence of the following events will be summarized:

- Local skin tolerance: incidence, severity and duration of local TEAE at site of Viaskin® application as reported by subjects in the diary card
- TEAEs: incidence, severity and duration.
- Potentially drug-related TEAEs
- Discontinuations due to TEAEs
- Laboratory data, physical examinations, and vital signs Systemic allergic symptoms in the active and placebo groups
- Potentially drug-related systemic allergic symptoms
- SAEs
- Potentially drug-related SAEs

In addition, TEAEs will be summarized by relationship to study drug and by severity. If a subject has more than one occurrence of the same TEAE with different severities or relationship to study drug, then the TEAE will be assigned to the highest severity category and/or most related relationship category. If the intensity or relationship is missing, then the 'worst case' will be assumed (i.e., severe for intensity and drug-related for relationship).

The proportion of subjects that experience systemic allergic symptoms will be summarized by treatment. All TEAEs will be listed.

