**Table 15 specifications**

Repeat with ITT population and PP population separately as Table 15A and Table 15B, respectively.

Table 16A. Detailed Listing for All Adverse Events by MedDRA System Organ Class

Adverse events were classified into SOC and PT using Version XX.0 of MedDRA.

The following coding will be used:

Severity: 1=Mild, 2=Moderate, 3=Severe, 4=Life-threatening, and 5=Death.

Grade: 1, 2, 3, and 4.

Causality: 1=Unlikely related, 2=Possibly related, and 3=Probably related.

Action taken: 0=None, 1=Prescribed medication, 2=Non-medication treatment, 3=Hospitalization or prolongation, 4=Discontinued treatment.

Outcome: 1=Ongoing (no change), 2= Recovering/resolving (improving), 3=Worsened, 4=Recovered/resolved with no sequelae, 5=Recovered/resolved with sequelae (chronic stable) 6=Death.

Table 16B. Detailed Listing for All Adverse Events by MedDRA Preferred Term

Adverse events were classified into SOC and PT using Version XX.0 of MedDRA.

The following coding will be used:

Severity: 1=Mild, 2=Moderate, 3=Severe, 4=Life-threatening, and 5=Death.

Grade: 1, 2, 3, and 4.

Causality: 1=Unlikely related, 2=Possibly related, and 3=Probably related.

Action taken: 0=None, 1=Prescribed medication, 2=Non-medication treatment, 3=Hospitalization or prolongation, 4=Discontinued treatment.

Outcome: 1=Ongoing (no change), 2= Recovering/resolving (improving), 3=Worsened, 4=Recovered/resolved with no sequelae, 5=Recovered/resolved with sequelae (chronic stable) 6=Death.

Table 17A. Adverse Events by System Organ Class (Number of subjects)

Adverse events were classified into SOC and PT using Version XX.0 of MedDRA.

Table 17B. Adverse Events by System Organ Class (Number of adverse events)

Adverse events were classified into SOC and PT using Version XX.0 of MedDRA.

Table 18. Summary of Adverse Events by Treatment Group

	All	Viaskin® milk	Placebo
Number of subjects (%) with AEs			
Number of AEs			
Number of AEs per subject			
0			
1			
2 +			
Number of systemic allergic symptoms			
Potentially drug-related			
Yes			
No			
Severity of AEs			
Mild			
Moderate			
Severe			
Life-threatening			
Death			
Serious AEs (SAEs)			
Yes			
No			
Number of potentially drug-related SAEs			
AE leading to discontinuation			
Yes			
No			
AE leading to death			
Yes			
No			
Ongoing			
Yes			
No			
Outcome			
Unchanged			
Worsened			
Recovered/resolved with no sequelae			
Recovered/resolved with sequelae			
Death			

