Table 19A. Treatment-Emergent AEs (TEAEs)\* by Treatment Groups  
(Number of subjects (%))

	All	Viaskin® milk	Placebo
TEAEs			
Potentially drug-related TEAE			
Severity of TEAE			
Mild			
Moderate			
Severe			
Life-threatening			
Death			
Serious TEAE			
TEAE leading to discontinuation			
TEAE leading to death			
Number of TEAEs			
0			
1			
2			
3 +			
Ongoing			
Yes			
No			
Outcome			
Unchanged			
Worsened			
Recovered/resolved with no sequelae			
Recovered/resolved with sequelae			
Death			

\* Treatment-emergent AE is defined as any AE, regardless of relationship to study drug, which occur during AE collection period of study drug or an event already present that worsens in either intensity or relationship to study drug following exposure to Viaskin®.

Table 19B. Treatment-Emergent AEs (TEAEs)\* by Treatment Groups  
(Number of TEAE)

	All	Viaskin® milk	Placebo
Number of TEAEs			
Number of potentially drug-related TEAE			
Number of severity of TEAE			
Mild			
Moderate			
Severe			
Life-threatening			
Death			
Number of serious TEAE			
Number of TEAE leading to discontinuation			
Number of TEAE leading to death			
Number of TEAEs per subject			
0			
1			
2			
3 +			
Number of local TEAE			
Number of severity of local TEAE			
Mild			
Moderate			
Severe			
Life-threatening			
Death			
Outcome			
Unchanged			
Worsened			
Recovered/resolved with no sequelae			
Recovered/resolved with sequelae			
Death			

\* Treatment-emergent AE is defined as any AE, regardless of relationship to study drug, which occur during AE collection period of study drug or any event already present that worsens in either intensity or relationship to study drug following exposure to Viaskin®.

Table 20. Summary Statistics of Local Skin Reactions (Adverse Events)

	All	Viaskin® milk	Placebo	
Number of patients with reactions				
0				
1				
2				
3				
4				

Values will be expressed as frequency counts (percentages) unless indicated.

Table 21. Summary of Laboratory Abnormalities based on CTC Grade by Visit and Treatment Groups

	Viaskin®Milk				Placebo				
	Visit 1	Visit 8	Visit 10	Visit 16	Visit 1	Visit 8	Visit 10	Visit 16	
Hematology									
RBC Count									
WBC Count									
Hemoglobin									
Hematocrit									
Platelet Count									
Segmented Neutrophils									
Lymphocytes									
Monocytes									
Eosinophils									
Basophils									
Chemistry									
Total Protein									
Blood Urea Nitrogen									
Creatinine									
ALP									

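### The SAP's adverse event listings have no code for two of the protocol's five causality levels, Unrelated and Related

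*SAP*

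**What the plan says.** Protocol 12.1 asks the investigator to rate each adverse event against treatment on five defined levels. The lowest, Unrelated, is for "those AEs which are clearly and incontrovertibly due to extraneous causes". Unlikely, Possible and Probable follow. The highest is defined apart from Probable: "an adverse experience may be considered related if it includes all of the following features". The fifth of those features is "It reappears or worsens if the drug is re-administered".

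Protocol 13.6.6.1 builds on that scale. It says "TEAEs will be summarized by relationship to study drug and by severity". If a child has the same event more than once at different levels, the highest level is used. If the relationship is missing, the event is taken as drug-related.

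SAP 4.5.1 names causality as an item in the adverse event listings and repeats the rule for a missing relationship. The listings are Tables 16A and 16B. Each carries the same key, introduced as the coding that will be used: "Causality: 1=Unlikely related, 2=Possibly related, and 3=Probably related". Tables 19A and 19B reduce relationship to a single row, labelled in Table 19A "Potentially drug-related TEAE". Table 18 has similar rows for systemic allergic symptoms and for SAEs. Neither document says which levels belong in those rows.

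**The concern.** The protocol collects five levels and the SAP can display three. The two that drop out are the informative ends of the scale: events that the investigator is sure the patch did not cause, and events that came back when the patch was re-applied.

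The top level can be reached in this trial. Under protocol 8.5.6, a patch removed for a severe local reaction is replaced by a new one the next day and the skin is watched: "If or when the local severe reactions recur, the patch can be removed at that time". Recurrence on re-administration can therefore be seen for local skin reactions, which are the main expected harm of the product.

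At stake is whether the listings report the investigator's judgement faithfully, and whether an event judged Unrelated could enter a drug-related count through the rule for missing values.

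**Working it through.** No sample size, power or event figure is involved, so the check is a comparison of the two scales, followed by tracing what happens to each level.

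**Step 1: match the levels.**

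| Protocol 12.1 level | Code in SAP Tables 16A and 16B |
|---|---|
| Unrelated | none |
| Unlikely | 1 |
| Possible | 2 |
| Probable | 3 |
| Related | none |

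Levels without a code: 5 − 3 = 2.

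**Step 2: trace the two uncoded levels.** Each can be forced into the nearest code or left blank. The last column applies the missing-relationship rule and assumes that the drug-related rows begin at Possible, a cut that neither document states.

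| Investigator's level | Handling | Listing shows | Counted as drug-related? |
|---|---|---|---|
| Unrelated | nearest code | unlikely related | no; count right, label wrong |
| Unrelated | left blank | nothing | yes; count and listing wrong |
| Related | nearest code | probably related | yes; count right, label too low |
| Related | left blank | nothing | yes; count right, level lost |

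All four routes give a wrong listing. One of the four also gives a wrong count: Unrelated left blank. If the cut began at Unlikely instead, the first route would miscount as well. The count therefore depends on a definition that the SAP leaves open.

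**Step 3: the rule for repeated events.** Suppose a child has the same skin reaction twice, rated Probable the first time and Related when it recurs on re-application. Protocol 13.6.6.1 assigns Related. The highest level available in the SAP key is probably related, so the protocol's rule selects a value that the listing cannot hold.

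**The case against.** The strongest reply is that the three codes are only a key under table shells in an appendix. Data capture follows protocol 12.1, which gives five levels, and SAP 4.5.1 lists causality without limiting its values. With about 22 children and no formal safety analysis planned, every event can be read individually. This largely stands: the documents do not show that any assessment would be lost from the database. It does not remove the point, because the key is complete, appears twice and is stated as the coding to be used. A programmer who follows it produces a wrong listing.

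The SAP also says that it rests on protocol 7.0, while the protocol supplied is 8.0. The scale in 7.0 cannot be checked, so the two may have agreed when the SAP was written. That could explain the mismatch, but the SAP would still need correcting.

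Four stronger readings are tempting, and the documents do not support them.

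- *A third causality scale.* The withdrawal rule in protocol 8.4.3.1 speaks of "Grade 4 local skin reactions possibly, probably, or definitely related to the investigational product". The last term there is a plain synonym for the top level.
- *A broken promise to summarise by relationship.* A drug-related row is such a summary, and protocol 13.6.6.1 itself lists potentially drug-related events among those to be summarised. The unstated cut is missing detail, not a contradiction.
- *A failure to separate endoscopy or anesthesia events from patch events.* No SAP table does this. But cases can be recognised from description, coded term and date. Protocol 12.2 considers research procedures in its definition of unanticipated problems, Appendix 3 names endoscopy risks apart from patch risks, and 12.3 has all SAEs reported whatever their cause. The eCRF and safety management plan, which are not in the documents, may hold a procedure item. The numbers are also small. There would be 18 × 2 = 36 to 22 + 18 = 40 research endoscopies. At the 1 in 29 rate in protocol 10.2, applied to every procedure as an assumption, that gives 36/29 = 1.2 to 40/29 = 1.4 events, mostly non-serious. A separate item would be an addition that needs an amendment under protocol 17.2.
- *40% of the safety data affected.* Two of five is a share of labels, not of events.

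**Conclusion.** The mismatch is real and is wrong as written: a stated coding rule cannot represent two of the five levels that the protocol tells investigators to use. It is a minor SAP correction.

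The definite effect is on the two listings. An effect on counts is conditional: an Unrelated event would have to be left uncoded, or the drug-related cut placed as low as Unlikely. The documents give no expected number of events at either level, so the number affected cannot be estimated. If one child were miscounted, that arm's rate would move by 1/16 = 6.3 points on active or 1/6 = 16.7 points on placebo. Any single reclassified child would have the same effect, so these figures show how small the arms are and do not measure this defect.

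The conclusion assumes that the five-level scale in protocol 8.0 is the one in use and that the printed key is the whole code list. The column layouts of Tables 16A and 16B are not visible in the text supplied, but the key is.

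**What to change.** In SAP Tables 16A and 16B, replace the causality key with the protocol's five levels. Coding them as 0 = Unrelated, 1 = Unlikely, 2 = Possible, 3 = Probable and 4 = Related leaves the three existing values unchanged. In the same edit, add one sentence to SAP 4.5.1 stating that Possible, Probable, Related and missing count as potentially drug-related, so that the cut is fixed before unblinding. When doing so, check the 12.1 scale in protocol 7.0 against that in 8.0.

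The cost is two code values and one sentence, made before the SAP is finalised ahead of database lock. It needs no protocol amendment, visit or new data item. The one possible extra is that, if the eCRF was built on the three codes, events already entered would need their level confirmed from source notes. The documents do not show whether that is so.

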## 5.2 Consort diagram

**Figure 1: Consort Diagram**
